7.4 Method, Frequency, and Time Period for Detecting AEs and SAEs

At each assessment, after the subject has had an opportunity to spontaneously mention any problems, the Investigator should inquire about AEs by asking the following questions:

1. Have there been any (other) medical problems since your last visit/assessment?"
2. Have any new medications been taken, other than those given to you in this study, since your last visit/assessment?"

7.4.1 Time Period for Detecting and Reporting of AEs and SAEs

The time period for detecting and reporting AEs and SAEs is from the time of informed consent through study completion/withdrawal, including the follow-up period.

7.4.2 Post-Study SAEs

Investigators are not obligated to actively seek SAE information in former study subjects, but Investigators are encouraged to notify the Sponsor/designee of any SAEs occurring at any time after a subject has discontinued or terminated study participation that they judge may reasonably be related to study treatment or study participation.

7.5 Documenting AEs and SAEs

All AEs that occur after the subject has signed the ICF through 28 days after last dose of study medication, regardless of causality or seriousness, will be assessed and recorded in the subject's

source documents and in the eCRF. If a subject is withdrawn during treatment, they must be followed for 28 days after the last dose as well. In addition, SAEs must be documented on the paper SAE Report Form.

The Investigator should attempt to establish a diagnosis for the event based on signs, symptoms, and/or other clinical information. In such cases, the diagnosis should be documented as the AE or SAE and not the individual signs/symptoms. When this is not possible, the AE should be documented in terms of signs and/or symptoms observed by the Investigator or reported by the subject at each study visit. Each AE which appears to be independent of any prior event will be reported separately.

For clinically significant abnormal laboratory findings or other abnormal assessments meeting the definition of an AE or SAE, a diagnosis, if known (or clinical signs and symptoms if a diagnosis is unknown), should be recorded by the Investigator. If a diagnosis is unknown and clinical signs and symptoms are not present, then the abnormal finding should be recorded. When documenting as an SAE on the SAE Report Form, relevant laboratory (including the reference range and units) or copies of the laboratory report (with reference ranges and units) should be sent with the SAE Report Form.

The SAE Report Form should be completed as thoroughly as possible and signed by the Investigator or his/her designee before transmittal to the Sponsor/designee. Investigators should not wait to receive additional information to fully document the event before notifying the Sponsor of an SAE. It is very important that the Investigator (or designee) provide his/her assessment of causality to study product at the time of initial SAE reporting.

7.6 Common Terminology Criteria for Adverse Events

The severity of events will be determined based on the Common Toxicity Criteria for Adverse Events (CTCAE), version 5.0. The CTCAE quick reference guide can be found at:

https://ctep.cancer.gov/protocolDevelopment/electronic_applications/docs/CTCAE_v5_Quick_Reference_8.5x11.pdf

For events not specifically addressed in the CTCAE, the following definitions should be considered when evaluating the severity of AEs and SAEs:

Severity of Event	
Grade 1	Mild; asymptomatic or mild symptoms; clinical or diagnostic observations only; intervention not indicated.
Grade 2	Moderate; minimal, local or noninvasive intervention indicated; limiting age-appropriate instrumental ADL*.
Grade 3	Severe or medically significant but not immediately life-threatening; hospitalization or prolongation of hospitalization indicated; disabling; limiting self-care ADL**.
Grade 4	Life-threatening consequences; urgent intervention indicated.
Grade 5	Death related to AE.
Activities of Daily Living (ADL)	

 * Instrumental ADL refer to preparing meals, shopping for groceries or clothes, using the telephone, managing money, etc. ** Self-care ADL refer to bathing, dressing and undressing, feeding self, using the toilet, taking medications, and not bedridden. 	

7.7 Assessment of Causality

The Investigator should assess the relationship of the AE, if any, to the study drug as either “Related” or “Not Related.”

- Related: There is at least a reasonable possibility that the AE/SAE is related to the study drug. Reasonable possibility means that there is evidence to suggest a causal relationship between the drug and the AE.
- Not Related: There is little or no reasonable possibility that the AE/SAE is related to the study drug. This assessment implies that the AE/SAE has little or no temporal relationship to the study drug and/or a more likely or certain alternative etiology exists.

The following should be considered when assessing AE/SAE causality:

- Positive temporal relationship to study drug, such as if study drug was withdrawn and the SAE resolved, or the event recurred after re-introduction,
- If there is a reasonable possibility that the AE is associated with an underlying or concomitant illness.

- Possible association with previous or concomitant therapy,
- No temporal relationship to treatment with study drug and/or a more likely alternative etiology exists.
- If the AE is directly related to study procedures.

7.8 Follow-up of AEs and SAEs

All AEs, regardless of seriousness, must be followed until resolution, until the condition stabilizes, until the event is otherwise explained, or until the subject is lost to follow-up. The Investigator is responsible for ensuring that follow-up includes any supplemental investigations as may be indicated to elucidate as completely as practical the nature and/or causality of the AE. This may include additional laboratory tests or investigations, histopathological examinations, relevant hospital records (i.e., discharge summary), or consultation with other health care professionals.

Salix may request that the Investigator perform or arrange for the conduct of supplemental measurements and/or evaluations. If a subject dies during participation in the study or during follow-up period, the Sponsor/designee should be provided with a copy of any postmortem findings, including histopathology.

If cause of death is not available within the 24-hour reporting period, “death” must be reported as SAE term to meet timelines and the cause of death actively queried and submitted as a follow-up report.

When additional SAE information becomes available, it should be recorded on a new SAE Report Form and should be labeled as a “Follow-up Report”. The original SAE Report Form should not be altered. All completed SAE Report Forms must be signed and dated by the Investigator or designee. By signing the SAE Report Form, the Investigator or designee attests to the accuracy and completeness of the data and that he/she has reviewed and approved the report being submitted. The investigational sites IRB/EC must be notified about SAEs in accordance with the requirements of the governing IRB/EC.

Patients should be monitored for development of Clostridium difficile-associated diarrhea (CDAD). If a patient develops severe, unremitting diarrhea, a diagnosis of Clostridium difficile-associated diarrhea (CDAC) should be considered and investigated. If CDAD is confirmed during the study, the interventional therapy will be stopped, and the subject will be discontinued from the trial. Symptoms of CDAD may be non-specific and indistinguishable from other causes of diarrhea, but if CDAD is suspected, study drug must be held until CDAD can be ruled out. If CDAD is confirmed, then the interventional therapy will be stopped, and the subject will be discontinued from the trial. CDAD must also be reported as an AE or SAE depending on presentation. Appropriate fluid and electrolyte management, protein supplementation, antibiotic treatment of C. difficile, and surgical evaluation should be instituted as clinically indicated.

7.9 Prompt Reporting of SAEs to Salix Pharmaceuticals, Inc.

SAEs must be reported promptly to the Sponsor/designee once the Investigator determines that the event meets the protocol definition of a SAE.

Prompt reporting of an SAE requires:

- Completion and transmission of the SAE Report Form to the Sponsor/designee via email or fax within 24 hours of the Investigator's knowledge of the event. In parallel, a corresponding AE with the SAE details should be entered into the AE eCRF within 48 hours of submitting the paper SAE Report Form.
- Prompt reporting of additional information for previously reported SAEs should follow the same reporting timeframe as initial reports. In addition, the corresponding AE in the AE eCRF (as applicable) should be updated to ensure all data points documented in the AE eCRF are aligned with the matching data points on the paper SAE Report Form.

7.10 Pregnancy Reporting

Pregnancies detected in subjects assigned to study treatment should be promptly reported to the Sponsor/designee via email/fax, using the Pregnancy Report Form, as soon as the Investigator is notified. If a female subject becomes pregnant following assignment to study treatment, the study drug will be immediately discontinued, and the subject will be followed until the outcome of the pregnancy is known. (Refer to the [Section 4.4](#)).

The Sponsor/designee should be notified via email/fax of any updates on the status of the pregnancy within 24 hours by completion of a separate follow-up pregnancy notification form. Outcome of pregnancy must be reported.

Although pregnancy occurring in a clinical study is not considered to be an AE or SAE, any pregnancy complication or elective termination of a pregnancy will be recorded as an AE or SAE and followed as such. If a pregnancy is associated with an SAE, an SAE Report Form should be forwarded to the Sponsor/designee within 24 hours of the Investigator's awareness, along with the Pregnancy Report Form.

7.11 Transmission of SAE Report Forms and Pregnancy Report Forms

Completed SAE Report Forms and completed Pregnancy Report Forms should be transmitted to the Sponsor/designee via the email address provided below:

7.12 Contraception Requirements

All women of childbearing (reproductive) potential and all men must practice effective contraception during the study and for 30 days after the last dose.

For the purposes of this study, women who do not meet one of the following criteria listed below are considered physiologically capable of becoming pregnant and are, therefore, defined as women of childbearing potential:

- Postmenopausal
- 24 months of natural (spontaneous) amenorrhea without an alternative medical cause
- 6 weeks after surgical bilateral oophorectomy with or without hysterectomy
- Post-hysterectomy
- Female surgical sterilization (e.g., bilateral tubal ligation)

For the purposes of the study, effective contraception is defined as use of 2 of the following for females:

- Oral contraceptives taken for at least 30 days prior to the Screening Visit and maintain contraceptive regimen throughout the study.
- Placement of a non-hormonal intrauterine device or intrauterine system.
- Barrier methods of contraception with use of a spermicide: condom or occlusive cap (diaphragm or cervical/vault caps) with spermicidal foam/gel/film/cream suppository. The use of barrier contraceptives should always be supplemented with the use of a spermicide.
- Male surgical sterilization (with the appropriate post-vasectomy documentation of the absence of sperm in the ejaculate).

For the purposes of the study, effective contraception is defined as use of 1 of the following for males:

- Effective male contraception includes a vasectomy with negative semen analysis at follow-up.
- The use of condoms with spermicide.
- Confirmation of birth control practiced by female partner with condom use.

True abstinence, when this is consistent with the preferred and usual lifestyle of the subject, can be considered an acceptable method of contraception based on the evaluation of the Investigator, who should also take into consideration the duration of the clinical trial. Periodic abstinence (e.g., calendar, ovulation, symptothermal, postovulation methods) and withdrawal are not considered acceptable methods of contraception.

8.0 STATISTICAL CONSIDERATIONS

Detailed methodology for statistical analyses of the data collected in this study will be documented in a Statistical Analysis Plan (SAP). The SAP will be finalized prior to database lock.

All continuous variables will be summarized using descriptive statistics; N, mean, standard deviation (SD), median, maximum, and minimum. All categorical variables will be summarized using frequency counts and percentages.

Baseline value is defined as last available value prior to the first dose of study drug.

EOT value is defined as last available post-Baseline value during the treatment period.

All data collected in the database will be presented in data listings.

8.1 Randomization

Subjects who meet the eligibility criteria and have given written informed consent will be randomized in a 2:2:1:2:2:1 allocation to one of six treatment groups as noted in [Section 3.2](#).

8.2 Sample Size

The total of 60 subjects is not based on formal statistical considerations. Twelve (12) subjects per group receiving active rifaximin is considered adequate to evaluate the PK/PD of rifaximin ER and DER.

8.3 Analysis Populations

The analysis populations will be defined as follows:

- Safety Population will include all subjects who have taken at least one dose of study drug.
- PK Population will include all subjects who have taken at least one dose of study drug and have sufficient data to calculate PK parameters for rifaximin and 25-desacetyl rifaximin.

Summarization of disposition, demography and Baseline characteristics, PD assessments, VOCs, and safety will be performed using the Safety Population. PK analyses will be conducted using the PK Population.

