8.4.4 Pharmacokinetics

Concentrations of rifaximin and its metabolite (25-desacetyl rifaximin) will be summarized by formulation and by dose. Concentrations will be summarized for samples taken for 8 and 72 hours after the initial dose and the final dose, respectively.

Dense sampling for initial dose (first dose interval): C_{max} , T_{max} , AUC_{last} , AUC_{0-8h} , and MR_AUC_{0-8h} , will be summarized.

Dense sampling for final dose: C_{max} , T_{max} , C_{min} , C_{avg} , AUC_{0-8h} , CL/Fss , Vz/Fss , R_{Cmax} , $R_{AUC\tau}$, AUC_{last} , AUC_{inf} , λz , $t_{1/2}$, and MR_AUC_{0-8h} , will be summarized.

Steady state levels will be summarized for all subjects based on C_{trough} on Day 8, Day 15, and Day 29.

Additional PK parameters maybe calculated if it deemed necessary.

LIST OF PHARMACOKINETIC TERMS

Parameter	Definition
AUC_{last}	Area under the plasma drug concentration-time curve from time 0 to the last quantifiable drug concentration
AUC_{inf}	Area under the plasma drug concentration-time curve from time 0 extrapolated to infinity

AUC _{0-8h}	Area under the plasma drug concentration-time curve from time 0 through 8 hours
C _{avg}	Average plasma concentration at steady-state
C _{max}	Maximum observed plasma concentration
C _{min}	Minimum observed plasma concentration
C _{trough}	Observed plasma concentration at the end of a dosing interval, just prior to the administration of the next dose
T _{max}	Time of maximum observed plasma concentration
t _{1/2}	Apparent terminal elimination half-life
λ _z	Terminal elimination rate constant
CL/F _{ss}	Apparent systemic extravascular clearance at steady-state
V _z /F _{ss}	Apparent extravascular volume of distribution during the terminal elimination phase at steady-state
R _{AUC}	Accumulation ratio of AUC _r at steady-state to AUC _{last} after the first dose
R _{Cmax}	Accumulation ratio of C _{max} at steady-state to C _{max} after the first dose
MR AUC	Metabolite-to-parent ratio for AUC

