8.4.13 Missing Data

Only available data will be analyzed. There will be no imputation of missing data.

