8.5.4 Noncompartmental Analysis of Rifaximin and 25-desacetyl rifaximin

NCA will be conducted for subjects using intensive PK samples collected at Visit 2 (Day 1) and Visits 5 to 8 (Days 29 to 32). PK parameters listed in Section 8.4.4 will be summarized using descriptive statistics, including number of observations, mean, median, CV%, SD, minimum, and maximum.

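### The single PK Population requires evaluable data for both analytes, so inadequate metabolite data can remove a usable rifaximin profile from the parent-drug summaries

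*Combined protocol and SAP*

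**What the plan says.** Section 8.3 (Analysis Populations) defines one PK Population. A subject must have taken at least one dose of study drug and must "have sufficient data to calculate PK parameters for rifaximin and 25-desacetyl rifaximin". The same section then states that "PK analyses will be conducted using the PK Population". No population specific to one analyte or one profile day appears elsewhere in the text.

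Section 8.4.4 covers both analytes: "Concentrations of rifaximin and its metabolite (25-desacetyl rifaximin) will be summarized by formulation and by dose". It lists different parameter sets for the first-dose and final-dose profiles. In that list only MR_AUC, defined as "Metabolite-to-parent ratio for AUC", needs parent and metabolite together. Section 8.5.4 gives the parameter summaries as "number of observations, mean, median, CV%, SD, minimum, and maximum".

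On incomplete data, section 8.4.13 says: "Only available data will be analyzed. There will be no imputation of missing data". The text gives no limit of quantification, no rule for concentrations below it, and no definition of sufficient data by parameter or day. Section 8.0 leaves detailed methods to a SAP to be finalised before database lock; no separate SAP is in the text reviewed here.

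**The concern.** The rule joins the two analytes. Followed as written, it discards a rifaximin profile because of a shortfall in the metabolite, and gains nothing for any parameter other than the ratio.

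The loss need not be random. If subjects with low metabolite exposure also tend to have low parent exposure, the rule selects on the quantity being estimated. The retained subjects would then show a higher mean and a smaller spread than the arm as randomised. If one assay limit applies to both doses, more subjects could be lost at 40 mg than at 80 mg, and the apparent increase with dose would be compressed.

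Characterising the PK is part of the first listed objective, and each active arm has 12 subjects, so one exclusion is 1/12, or about 8% of an arm. Because profile day is not mentioned, it is also unclear whether a subject who stops before Day 29 keeps a place in the Day 1 summaries.

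**Working it through.** **The plan's own figure.** Section 8.1 states that subjects are "randomized in a 2:2:1:2:2:1 allocation to one of six treatment groups". With 60 subjects and ratio parts summing to 10: 60 × 2/10 = 12 per active arm and 60 × 1/10 = 6 per placebo arm; 4 × 12 + 2 × 6 = 60. This reproduces. Section 8.2 says the total has no formal statistical basis, so there is no power calculation to check.

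**Model for the exclusion.** Parent and metabolite exposure are taken as jointly log-normal, and subjects with the lowest metabolite exposure are excluded. All three inputs are assumptions, because the documents give none of them:
- CV, the between-subject CV of parent exposure: 40%, 60%, 100%
- ρ, the log-scale correlation of parent and metabolite: 0, 0.3, 0.6, 0.9
- f, the share of an arm excluded for inadequate metabolite data: 10%, 25%, 50%

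Let s = √ln(1 + CV²), let z be the standard normal quantile of f, and let Φ and φ be the normal distribution function and density. Retained value divided by full-arm value:
- arithmetic mean ratio A = Φ(ρs − z)/(1 − f)
- geometric mean ratio G = exp[ρs·φ(z)/(1 − f)]
- retained CV = √{exp(s²)·Φ(2ρs − z)/[(1 − f)A²] − 1}

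**Middle case (CV 60%, ρ 0.6, f 25%).** s = √ln 1.36 = 0.5545; ρs = 0.3327; z = −0.6745.
- A = Φ(1.0072)/0.75 = 0.843/0.75 = 1.124
- G = exp(0.3327 × 0.3178/0.75) = 1.151
- retained CV = √[1.36 × 0.910/(0.75 × 1.124²) − 1] = 0.553, which is 0.92 of the true 0.60
- subjects left: 12 × 0.75 = 9

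A simulation of 2,000,000 draws gave 1.123 and 1.151 for the two means.

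**Range.**

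| CV | ρ | f | Left of 12 | Arithmetic mean ratio | Geometric mean ratio | Reported / true CV |
|---|---|---|---|---|---|---|
| 40% | 0.3 | 10% | 10.8 | 1.021 | 1.023 | 0.99 |
| 60% | 0 | 25% | 9 | 1.000 | 1.000 | 1.00 |
| 60% | 0.6 | 10% | 10.8 | 1.052 | 1.067 | 0.96 |
| 60% | 0.6 | 25% | 9 | 1.124 | 1.151 | 0.92 |
| 60% | 0.6 | 50% | 6 | 1.261 | 1.304 | 0.88 |
| 40% | 0.9 | 50% | 6 | 1.271 | 1.319 | 0.73 |
| 100% | 0.9 | 50% | 6 | 1.546 | 1.818 | 0.75 |

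Section 8.5.4 lists the arithmetic mean and not the geometric mean, so the arithmetic column is the relevant one: +2% to +55%.

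**Dose.** Two further assumptions: one assay limit serves both doses, and exposure doubles with dose. In the middle case, 25% lost at 40 mg moves the cut-off at 80 mg to z = −0.6745 − ln 2/0.5545 = −1.9245, so 2.7% are lost there. The 80 mg arithmetic ratio is Φ(0.3327 + 1.9245)/0.973 = 0.988/0.973 = 1.016. A true two-fold ratio of means then appears as 2 × 1.016/1.124 = 1.81. On the geometric scale it appears as 1.775, and as 1.43 to 1.91 across CV 40-100%, ρ 0.3-0.9 and 25-50% lost at 40 mg.

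**After the fix.** With eligibility set by analyte, this rule removes no subject from the parent summaries. Up to 12 per active arm remain and the ratio is 1.00.

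**The case against.** A reader might infer that low-exposure subjects will drop out and that the reported rifaximin PK is therefore too high. The documents do not support that. They do not say that the metabolite will be unquantifiable in anyone, and they give no metabolite level and no correlation. The upward direction in the calculation comes from assuming ρ above zero and removing the lowest metabolite values. This part of the objection stands in full.

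Sufficient data is also undefined. AUC to the last quantifiable concentration and Cmax may need only a few quantifiable values, and a fully sampled subject whose low values are set to zero might qualify. A team could apply the joint wording analyte by analyte. The available-data statement in 8.4.13 fits that practice, the number of observations in 8.5.4 would make any loss visible, and the separate SAP may settle the question. These points make a silent loss less likely. They do not change what 8.3 says, and no analyte-specific reading is written down.

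On materiality, one standard error of the mean for 12 subjects at CV 60% is 60%/√12 = 17%, larger than the middle-case bias of 12%. That is a fair limit for a descriptive study. However, a bias of the same sign in every arm does not average out, and this one is avoidable.

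A reader might also infer that the ER-versus-DER comparison is distorted. That would require different metabolite losses by formulation. The documents give no basis for this, and they plan no formal ER-versus-DER test of PK.

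**Conclusion.** The point holds as a defect in the eligibility rule, not as a demonstrated wrong number. Section 8.3 states a joint condition that only MR_AUC needs. Applied literally, it can remove usable rifaximin profiles from arms of 12.

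An upward bias in the parent mean and a reduced CV follow only if some subjects lack adequate metabolite data and parent and metabolite exposure are positively correlated. Under the assumed ranges the arithmetic mean rises by 2-55%, about 12% in the middle case, and the reported CV is 0.73 to 0.99 of its true value. A greater effect at 40 mg needs the further assumption of one assay limit for both doses. With no metabolite loss there is no effect; with zero correlation the only cost is fewer subjects. The actual size cannot be determined from the documents. Label: cheap improvement.

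**What to change.** In section 8.3 and in the SAP, define PK eligibility separately for each analyte and profile day: at least one dose of rifaximin, and sufficient data to calculate at least one parameter of that analyte on that day. Require evaluable data for both analytes only for MR_AUC.

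State before unblinding how concentrations below the quantification limit are handled in the concentration summaries and in the noncompartmental analysis. Without that rule, the metabolite and ratio summaries would still depend on an unstated choice about low values, even with analyte-specific sets.

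The cost is a few sentences. No visit, sample or treatment changes. N will differ by analyte and day across tables, so each table should show its own N.
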